9.4 Interim Analyses and Stopping Rules

We are not planning to conduct interim analyses due to the small sample size of this pilot study. The study is powered to require the full sample to assess efficacy. We do not anticipate any safety considerations that would warrant early discontinuation of the study. However, in the event that there are a high number of SAEs, the DSMB will guide the PI and study team on how to best proceed. Other study performance metrics (e.g., slow accrual, high losses-to-follow-up, and poor quality control) will be monitored by NCCIH and the DSMB.

9.5 Outcomes

The blinded assessors will collect the primary outcome of interest, IDS-CR. The Advisory Committee and DSMB will be unblinded.

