6.2.3 Blinding

The study clinician-assessors will be blinded. The research assistant welcoming the subject will remind the subject not to unblind the assessors at each assessment visit. Blinded assessors will complete all primary and secondary endpoint collection.

The randomization scheme will be executed by our biostatistician who will be blinded to treatment assignment and will also have no influence on outcome assessments. Our biostatistician will establish the blind and deliver it to the designated research assistant for this study. The Principal Investigator (PI) will not be blinded, since the PI will be delivering the psychoeducation preparatory visit (pre-yoga start) and also will be performing the bi-weekly phone monitoring. The PI will not have access to the data until the study database is locked. The DSMB identified in the submission will have access to unblinded data and will monitor adverse and serious adverse events.

Breaking the Blind: the PI, [name], and Medical Monitor, [name], are both unblinded to the intervention arm of each subject. In the event of a medical AE/SAE, [name] or his designee will be responsible for assuring safety of the patient. In the event of a psychiatric AE/SAE, [name] or her designee will be responsible for assuring the safety of the patient.

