7.6 Safety Monitoring

A data safety monitoring board (DSMB) has been assembled prior to the start of the study. The board consists of three staff-level investigators who are not key personnel involved with this grant. They are qualified to review the patient safety data generated by this study. One has expertise in mind-body interventions ([name], PhD); the second has expertise in clinical trial design ([name]); the third has expertise as a statistical consultant ([name]). The DSMB will meet at least quarterly per year to review study progress, address any difficulties with recruitment, and address any safety related matters that may arise. Details of the logistics of the DSMB are as follows:

- a. Unblinded Reporting** – Safety information for this study will be reported to the DSMB in an unblinded manner. A statistical penalty will not be assessed for the ongoing unblinded review of safety by the DSMB. Unblinded data will not be released to the investigators unless necessary for safety reasons.
- b. Range of Safety Reporting to the DSMB** – It is considered necessary for the purpose of monitoring the safety of the study that the DSMB review not only AEs and SAEs, but other data that may reflect differences in safety between treatment groups. This

includes treatment retention rates, reasons for drop-out, and laboratory values reflecting potential danger to patient.

- c. **Serious Adverse Events** – Expedited review will occur for all events meeting the FDA definition of SAEs. This also includes any event that a study investigator or the DSMB judges to impose a significant hazard, contraindication, side effect, or precaution.
- d. **Non-Serious Adverse Events** – At periodic intervals (quarterly during the course of the study and then again at its completion), the DSMB will be provided with un-blinded summaries of the numbers and rates of adverse events by treatment group. These reports will include types of events, severity, and treatment phase. Data on individual non-serious adverse events is not expected to be needed for this review.
- e. **Other Safety-Related Reports** – At twelve-month intervals throughout the course of the study, the DSMB will also receive unblinded summary reports of treatment retention and reasons for drop-out, by treatment arm and study phase.

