12. COMMITTEES

Advisory Committee: All mentors (Drs. [name], [name], and [name]) will meet quarterly as an Advisory Committee throughout the PI's K23 Award. The committee will provide guidance such that the following goals are met: 1) recruitment does not fall below 75% of projection, 2) treatment adherence is sufficient, and 3) authorship and future grant submission goals are met. [name] will oversee the PI's formal progress evaluations.

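### Section 9.5 unblinds the Advisory Committee of mentors on the same terms as the DSMB, with no limit on what it may see, and this does not match the blinding rules in section 6.2.3

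*Combined protocol and SAP*

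**What the plan says.** Section 9.5 (Outcomes) says that blinded assessors collect the IDS-CR, the primary outcome of interest. It then adds: "The Advisory Committee and DSMB will be unblinded". It gives no scope, timing or reason.

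Section 12 (Committees) identifies the committee as all the mentors, who "will meet quarterly as an Advisory Committee throughout the" PI's award. "The committee will provide guidance such that the following goals are met": the first goal is that "recruitment does not fall below 75% of projection", and the others are sufficient treatment adherence and the authorship and grant goals. Neither safety review nor efficacy review is listed. The primary mentor and co-mentors are on the study team roster at the front of the document. Section 10.3.4 has the PI and at least one mentor review protocol deviations with a view to amendment. Section 13 puts publication under policies that the committee develops.

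Three other statements bear on the point:

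- Section 6.2.3 (Blinding) gives access to unblinded data to the DSMB and names no other body. It says of the PI: "The PI will not have access to the data until the study database is locked". It also says that the PI and the medical monitor know each subject's arm.
- Section 7.6, item a, says "Safety information for this study will be reported to the DSMB in an unblinded manner" and then "Unblinded data will not be released to the investigators unless necessary for safety reasons".
- Section 9.4 says "We are not planning to conduct interim analyses due to the small sample size of this pilot study".

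**The concern.** A DSMB may see data by arm because it is separate from the people who run the trial. Section 7.6 makes that separation explicit: its members are not key personnel on the grant. The Advisory Committee has no such separation. It advises the PI on running the trial, shares in decisions that can lead to amendments, and has future grant submission among its goals. Section 9.2 gives the main purpose of the pilot as estimating an effect size for a larger grant application, so the committee has a direct interest in the emerging effect.

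Several analysis choices are left open in section 9.6. Baseline differences are to be adjusted for where this is judged necessary. The missing-data method depends on what the missingness looks like. Potential covariates, attendance among them, are to be examined. If advisers could know outcomes by arm while these choices remain open, nobody could later show that the choices, or an amendment, were made independently of the results.

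**Working it through.** The point rests on the text rather than on a figure, so the check is to set the statements side by side.

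**Step 1. Who is unblinded, and to what?**

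| Party | Knows arm | Sees data before lock | Where |
|---|---|---|---|
| DSMB | Yes | Yes, including summaries by treatment group | 6.2.3, 7.6, 9.5 |
| PI | Yes | No | 6.2.3 |
| Medical monitor | Yes | Not stated | 6.2.3 |
| Unblinded assessors | Yes | No, and no role in monitoring or analysis | 5.2 |
| Research assistant | Yes; collects attendance | Not stated | 5.2 |
| Advisory Committee | Yes (unblinded, no limit given) | Not stated | 9.5 only |

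**Step 2. What does the word mean in section 9.5?** The plan uses it in two senses. For the PI and medical monitor, section 6.2.3 ties it to the intervention arm. For the DSMB, it means data. Section 9.5 applies one predicate to the committee and the DSMB together and adds no restriction. Read as written, the committee stands on the DSMB's terms. Read narrowly, it knows arm only. The text does not settle which is meant.

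**Step 3. Does either reading fit section 6.2.3?** No. That section names the DSMB for unblinded data, and the PI and medical monitor for arm. It does not mention the Advisory Committee in either role. The two sections need reconciling whichever sense was intended.

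**Step 4. Does it fit section 7.6?** The release rule in item a is written about safety information reported to the DSMB, and the plan does not say whether mentors count as investigators. If they do, and if section 9.5 means data by arm, the two conflict. If either condition fails, they do not.

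**Step 5. Does the committee need outcomes by arm?** Recruitment can be judged from pooled counts, adherence from attendance, and authorship and grant planning from neither. Section 9.4 already assigns accrual, losses to follow-up and quality control to NCCIH and the DSMB, and section 7.6 assigns safety to the DSMB.

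**Step 6. Does a correction affect the design figures?** Section 9.2 gives 79% power at d = 0.70 and 50% at d = 0.50, with 32 per arm and two-sided alpha .05. The noncentrality parameter is d × √(n/2) = d × √16 = 4d, that is 2.80 and 2.00, on 2 × 32 − 2 = 62 degrees of freedom. The noncentral t distribution gives 78.7% and 50.4%, so the stated figures reproduce. None of these inputs depends on what the committee sees, so the correction leaves sample size, power and alpha as they are.

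**The case against.** The best defence is that being unblinded need not mean seeing results. The PI knows every subject's arm yet has no data until lock, and section 5.2 treats unblinded assessors in the same way. The sentence in section 9.5 follows one about blinded assessors, so knowledge of allocation is a natural reading. Overseeing adherence may require knowing who was assigned to yoga. No section sends outcome data to the committee.

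There are also real safeguards. IDS-CR assessors are blinded, a blinded coordinator manages the assessment data (10.1), the statistician reviews data quality blinded (10.2), and the analysis populations and the time-by-condition model are stated in advance (9.3, 9.6). This is a pilot whose participants know their assignment.

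Much of this stands. It rules out two stronger readings that a reader might infer:

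- **That section 9.5 flatly contradicts the release rule in 7.6 or the bar on the PI in 6.2.3.** The first rule concerns DSMB safety reporting and leaves investigators undefined. The second binds the PI only, and another body being unblinded does not breach it.
- **That quarterly meetings amount to hidden interim analyses that inflate type I error.** Section 9.4 says none are planned. The committee is given no comparison, test, decision rule or stopping power. Looking at data without a test or decision rule spends no alpha, so calculations for repeated tests at .05 do not apply.

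The defence does not remove the gap. Where the plan means arm only, it says so. Where it unblinds other people close to the trial, it mostly adds a limit on data access. For this committee it does neither. The blinded roles protect measurement and data handling, but they do not protect the choices that section 9.6 leaves open.

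**Conclusion.** The concern holds as an unrestricted permission with a missing firewall. Section 9.5 places a committee drawn from the study team on the DSMB's footing and sets no limit, while section 6.2.3 leaves that committee out and keeps the PI it advises from the data until lock. Tension with section 7.6 arises only if mentors count as investigators and unblinded means data by arm.

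The consequence is a risk of operational bias, which cannot be quantified from the documents. It depends on the committee actually being shown outcomes by arm, which the text permits but does not describe. No breach of section 9.4 and no inflation of type I error is shown, and no design figure changes. The change should be made because it is nearly free and because the study's main product is an effect estimate for a later trial. It is not a ground for doubting the design.

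**What to change.** Replace the sentence in section 9.5 with:

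*Before database lock, only the DSMB may see outcome data by arm; the Advisory Committee receives recruitment and retention pooled across arms, and summary class attendance without outcome data.*

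Then align the related sections:

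- **6.2.3:** add the Advisory Committee and repeat the same limit.
- **7.6, item a:** say that the investigators, for the release rule, include the mentors.
- **12:** list what the committee receives at its quarterly meetings.

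Leave unchanged the statements that the PI, medical monitor and research assistant know arm. A blanket statement that only the DSMB is unblinded would contradict sections 5.2 and 6.2.3. Attendance should reach the committee in summary form, because before crossover only the immediate group is assigned classes and individual records would reveal arm.

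If the sponsor does want the mentors to see outcomes by arm before lock, the plan should say so, give the reason, and state what stops the results reaching the PI.

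The cost is one replaced sentence and three short alignments. The downside is that the mentors do not see outcomes by arm until lock, which none of their listed goals requires.

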9.5.1 Primary Outcome

Primary Outcome Measures

Acceptability Interview (primary aim I): A 19-question qualitative interview assesses perception of ease of participation, program likeability, and perceived benefits of the yoga program. Adapted from DeBoer et al.³⁴.

Inventory of Depressive Symptomatology (IDS-CR): A valid and reliable 30-item measure that is designed to assess severity of depression. The questions focus on neurovegetative and other depressive symptoms experienced over the past seven days. Higher scores indicate more severe pathology. A decrease of 50% or more in the IDS-CR score is considered to be a positive response to treatment, while a final score of 11 or less is considered typical remission.

9.5.2 Secondary Outcomes

Secondary Outcome Measures

Spielberger State-Trait Anxiety Inventory (STAI)⁸⁴: A 40-item commonly used measure that distinguishes between state vs. trait anxiety.

Hamilton Depression Rating Scale (HAM-D-28)⁸⁵: A 28 item scale commonly used as an observational rating measure of depression presence and severity.

Medical Outcomes Study 36-item short-form survey (SF-36)⁸⁶: Assesses bodily pain, general health perception, vitality, social functioning, physical and emotional impediments to role functioning, mental health, and includes an overall physical component scale (PCS) and mental component scale (MCS). Used in a trial of yoga for women in breast cancer treatment⁸⁷.

Quality of Life Satisfaction Questionnaire-Short Form (Q-LES-Q-SF)⁸⁸: A measure of satisfaction and enjoyment in various domains.

Exercise Induced Feeling Inventory (EIFI)⁸⁹: Assesses feeling states associated with physical activity: Positive Engagement, Revitalization, Tranquility, and Physical Exhaustion. Sensitive to changes over the course of yoga treatment⁹⁰.

The Perceived Stress Scale (PSS)³⁸: Measures perceived level of stress.

University of Rhode Island Change Assessment Scale (URICA): Assesses participants' readiness to change.

Psychological Mechanisms of Actions

Sleep Diary: Includes a Stanford Sleepiness Scale rating⁹¹, in addition to tracking caffeine, alcohol, smoking, exercise and naps.

Pittsburg Sleep Quality Index (PSQI)⁹²: A commonly used and well-validated self-rated measure of sleep-quality and disturbance.

The Five Facet Mindfulness Questionnaire (FFMQ)⁹³: A self-report instrument that measures mindfulness; derived from factor analytic study of five independent mindfulness questionnaires.

Ruminative Responses Scale (RRS)³⁷: A 22-item questionnaire, which assesses depressive rumination style.

Potential Moderator

Hot Yoga Beliefs Scale: Adapted from the *Acupuncture Beliefs Scale*⁵⁵, a 36-item self-administered instrument that to determine positive and negative beliefs about the study therapy. The data from this questionnaire can be used to assess how patient beliefs and

clinical improvement may impact each other. For this study, the scale's questions have been adapted to reflect heated yoga rather than acupuncture as the therapy of interest.

Physiological Mechanisms of Action

Salivary Cortisol⁸⁷: Saliva will be collected using salivettes. To account for diurnal variation, four samples will be obtained prior to each cortisol assessment (nighttime [1 and 2] and waking [3 and 4]).

Inflammatory Markers: 30 mL of blood will be drawn per visit. 3 cc and 8 cc tubes will be used. Tubes will be centrifuged at 1500 rpm for 10 min at 4oC. Plasma will be transferred into 2 cc plastic tubes, capped and frozen at -80oC until processing. Levels of IL-6 and TNF-alpha cytokines will be assayed using commercially available radioimmunoassay or enzyme-linked immunosorbent assay at the Behavioral Neuroendocrinology Laboratory at the University of Colorado Boulder, led by [name]. Hs-CRP will be assayed at [name] lab using immunochemiluminometric assay (ICMA). These three markers have been heavily implicated in the pathophysiology of depression ^{58, 94} and shown to improve with yoga⁵⁹. [name] add-on study, supported by her Reich award, will be performing RNA-sequencing and analysis of the neurosteroids allopregnanolone and progesterone. The RNA-sequencing will be performed by Genewiz, and the neurosteroid data will be processed by the PK/PD Bioanalytical Core Facility located at the UC Davis Medical Center.

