Thermal Therapy for Depression: Whole-body hyperthermia is receiving attention as an antidepressant. A large effect size (*d*=1.13) was found 5-days post a single total-body hyperthermia session (mean time 126.7 minutes) in 16 medically healthy adults with MDD on the Centers for Epidemiological Studies Depression Scale (CES-D). Only 3 of the 16 subjects were on antidepressants (SSRIs). When the 13 SSRI-free subjects were analyzed separately, the effect sizes increased (*d*=1.4). These findings are consistent with studies of mood induced hyperthermia in medically ill populations^{23, 40}. In another study, fever induction in medication-free patients with melancholic MDD produced improvements in mood for all patients the day after induction, perhaps via inflammatory cytokines suppressing REM sleep, thus improving mood²⁴. In another study, 28 medication-free patients with mild depression and somatic complaints randomized to 4 weeks of 5x/week (20 sessions) thermal therapy vs. non-thermal therapy (60°C for 15 minutes followed by 30 minutes of bed rest with blanket) demonstrated improvement in somatic and mental complaints, hunger, and relaxation²¹. Other preliminary data also support heat's beneficial effect on mood^{17-19, 22}. Recent data suggest that Bikram Yoga similarly raises core body temperature¹⁵. There is evidence for a relationship between thermal regulation and serotonergic neural circuits controlling cognitive function and mood⁴¹. Depressed patients have disruption in thermoregulatory cooling, implicated in the maintenance of the disease⁴². Bikram Yoga offers both a mechanism for understanding this interaction and a means of treatment.

Yoga's Effects on the Stress Response Systems: Depression is linked to the body's physiological reaction to stress⁴³. Yoga may restore homeostasis by increasing

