Yoga and Secondary Outcomes: Anxiety: Symptoms of anxiety are often 40-50% comorbid with MDD⁷⁴⁻⁷⁶. Yoga may treat anxiety, though similar to the depression and yoga literature base, studies are methodologically flawed⁷⁷. **Sleep**: Sleep disturbance and depression have been linked to fragmentation of sleep architecture and likely share common biological pathways⁷⁸. Experienced Bikram Yoga practitioners using transition analysis had a faster return to sleep after nocturnal awakenings on nights when yoga was practiced that day compared to non-yoga days⁷⁹. Bikram Yoga may directly and/or indirectly improve mood by simultaneously improving sleep. Improved sleep regulation, via improved sleep efficiency and quality, may be a mechanism for yoga's antidepressant effects⁹.

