5.4 Adherence Assessment

Participants are asked to attend at least two weekly hyperthermic yoga classes over an 8-week intervention, a minimum total of 16 yoga classes. Adherence will be defined at 75% of the minimum prescribed dose of the study intervention – i.e., adherence means that participants attended at least 12 out of 16 yoga classes over the 8-week study intervention period. The two yoga studios track attendance via computer systems. Attendance data will be collected by study staff (usually a research assistant) who will either email via Send Secure email, or utilize Dropbox to communicate with the studio owners, [name] (Bikram Yoga Boston) and [name] (Bikram Yoga Cambridge), to obtain attendance data. All yoga students, whether study participants or not, are required to sign in at the front desk of the studios prior to class.

Yoga instructors act as front desk attendants for their own classes and sign participants into the computer system at this time.

Fidelity Assessment: The adherence of each of the two Bikram Yoga studios to the Bikram Yoga protocol will be established, prior to starting the proposed study and every six months thereafter with an adherence measure designed by [name].

Temperature Measurement: We will measure the temperature and humidity in the three heated yoga rooms with HOBO Bluethooth Low Energy Temperature/Relative Humidity Data. HOBO MX1101 data logger measures and transmits temperature and relative humidity data wirelessly to mobile devices via Bluetooth Low Energy (BLE) technology. These devices will be mounted in each of the three rooms. Study staff will collect data prior to study initiation and quarterly thereafter to monitor temperature and humidity- and to store the data for later analyses. These devices provide wireless and time stamped temperature and humidity data to smart phone device. The self-contained wireless data logger works with Onset's free HOBOmobile app for logger setup and data management. Data is accessible anytime from a mobile device for iOS or Android over a 100-foot range.

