6.2.2 Enrollment, Baseline, and/or Randomization

Enrollment

Enrollment is defined as the date all of the screening criteria are met— occurring between screening (visit 1) and baseline (visit 2).

Baseline Assessments (Visit 2 for IYG; Visits 2 and 7 for DYG)

At this visit subjects will meet with a study clinician for a 50-minute psychoeducational (see First Heated Yoga Class: What to Expect) and motivational session. Subjects will be asked to discuss reasons for wanting to try the hyperthermic yoga and also to discuss potential barriers to participation.

Visit 2: Baseline - IYG and DYG

- IDS-CR
- HAM-D-28
- Self-Rated Questionnaires: STAI, SF-36, Q-LES-Q, EIFI, PSS, PSQI, FFMQ, RRS, URICA
- Concomitant Medications
- Vital Signs
- Psychoeducational Session
- Waist-to-Hip Ratio
- Physiological Markers (i.e., inflammatory markers [blood], cortisol [saliva])
 - Please see section 9.5.2 for details
- Collect Sleep Diary (can bring to the following visit as long as it was completed for the right week)
- Collect salivates (can bring to the following visit as long as it was collected at the right time period)
- Adverse Events
- Hot Yoga Beliefs Scale

Visit 7: Repeat Baseline - DYG

- IDS-CR
- HAM-D-28
- Self-Rated Questionnaires: STAI, SF-36, Q-LES-Q, EIFI, PSS, PSQI, FFMQ, RRS, URICA
- Concomitant Medications
- Vital Signs
- Psychoeducational Session (refresher)
- Waist-to-Hip Ratio
- Physiological Markers[^] (i.e., inflammatory markers [blood], cortisol [saliva])
- Collect Sleep Diary (can bring to the following visit as long as it was completed for the right week)
- Adverse Events

- Hot Yoga Beliefs Scale

[^]If this visit takes place within 14 days of Visit 6, Physiological Markers will not be repeated at this visit.

At the end of the Baseline Visit that occurs before they start the yoga (V2 or V7), participants will be handed a packet of self-rated questionnaires (i.e. STAI-State and EIFI) to complete within 30 minutes prior and 30 minutes post each yoga class they attend. We will ask participants to note time and date on the top of each form. These questionnaires will provide data on acute mood changes pre- and post-yoga. [name] co-mentor [name] uses these questionnaires to gather the same data in her RO1 (5R01AT007483-05). Including this will allow us to compare data across studies.

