6.2.4 Follow-up Visits

Phone visits will occur bi-weekly from baseline through the end of the study intervention period. During the 1 month follow-up period, there will be a phone call during the midpoint (2-weeks into the follow-up period).

Assessment visits will be completed within a reasonable time frame (+/- 3 workday window), but may occur outside this window if deemed appropriate by study staff.

Visit 3 (Week-1 Assessment)* – IYG and DYG

- IDS-CR
- Self-Rated Questionnaires: STAI, SF-36, Q-LES-Q, EIFI, PSS, PSQI, FFMQ, RRS
- Concomitant Medications
- Vital Signs⁺
- Adverse events

Visit 4 (Week-3 Assessment)* – IYG and DYG

- IDS-CR
- Self-Rated Questionnaires: STAI, SF-36, Q-LES-Q, EIFI, PSS, PSQI, FFMQ, RRS
- Concomitant Medications
- Vital Signs⁺
- Give salivettes
- Give Sleep Diary (can bring to the following visit as long as it was completed for the right week)
- Adverse Events

Visit 5 (Week-5 Assessment) – IYG and DYG

- C-SSRS since Last Visit
- IDS-CR
- Self-Rated Questionnaires: STAI, SF-36, Q-LES-Q, EIFI, PSS, PSQI, FFMQ, RRS
- Concomitant Medications
- Vital Signs
- Waist-to-Hip Ratio
- Physiological Markers (i.e., inflammatory markers [blood], cortisol [saliva])
- Give salivettes
- Collect and give Sleep Diary (can bring to the following visit as long as it was completed for the right week)
- Adverse Events

Visit 8 (Week-1 Yoga Assessment) – DYG

- IDS-CR
- Self-Rated Questionnaires: STAI, SF-36, Q-LES-Q, EIFI, PSS, PSQI, FFMQ, RRS
- Concomitant Medications
- Vital Signs⁺
- Adverse Events

Visit 9 (Week-3 Yoga Assessment) – DYG

- IDS-CR
- Self-Rated Questionnaires: STAI, SF-36, Q-LES-Q, EIFI, PSS, PSQI, FFMQ, RRS
- Concomitant Medications
- Vital Signs⁺
- Give salivettes
- Give Sleep Diary
- Adverse Events

Visit 10 (Week-5 Yoga Assessment) – DYG

- C-SSRS since Last Visit
- IDS-CR
- Self-Rated Questionnaires: STAI, SF-36, Q-LES-Q, EIFI, PSS, PSQI, FFMQ, RRS
- Concomitant Medications
- Vital Signs
- Waist-to-Hip Ratio
- Physiological Markers (i.e., inflammatory markers [blood], cortisol [saliva])
- Give salivettes
- Collect and give Sleep Diary (can bring to the following visit as long as it was completed for the right week)
- Adverse Events

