Primary Aim II: To collect the Inventory of Depressive Symptomatology – Clinician Rated (IDS-CR) scores at screening; baseline; and weeks-1, -3, -5 and -8 to evaluate the efficacy of hyperthermic yoga for depressive symptoms.

Hypothesis II: The IYG will have greater decreases in Inventory of Depressive Symptomatology – Clinician Rated (IDS-CR) scores after 8-weeks compared to the DYG.

Response over 8-weeks defined by 50% or greater decrease on IDS-CR total; remission ≤ 11 on IDS-CR total. Continuous variables will be analyzed by generalized mixed effect modeling, which impute missing values based on maximum likelihood estimates of missing parameters, allowing analysis of all MITT participants. A time-by-condition interaction will be analyzed to test the intervention's efficacy. Relevant potential covariates (e.g., attendance) will also be examined.

Primary Aim III: To collect (a) physiological and (b) psychological mediators of hyperthermic yoga in the IYG and DYG group at screening; baseline; weeks-1, -3, -5 and -8 to evaluate treatment response in the IYG compared to the DYG.

Hypothesis IIIa: Salivary cortisol, and inflammatory markers (i.e., Tumor Necrosis Factor [TNF- α], Interleukin-6 [IL-6], and C-Reactive Protein [CRP]) will significantly decrease, following 5- and 8-weeks of hyperthermic yoga in the IYG compared to the DYG.

Hypothesis IIIb: Perceived stress, mindfulness, and rumination will improve by 5- and 8-weeks in the IYG compared to the DYG.

Latent growth curve modeling will assess potential mechanisms of the treatment effect. The slope (change over time) of the mediator variables will be regressed upon the independent variable (condition). The slope of the dependent variable will also be regressed upon the slope of the mediators. This model will permit assessment of the change in mechanisms as it predicts the change in the dependent variables.

Secondary Aim I: To collect measures of quality of life, general health, physical functioning, decreased perceived stress, anxiety, and sleep in the IYG and DYG at screening; baseline; and weeks-1, -3, -5 and -8 to evaluate hyperthermic yoga for secondary outcome measures.

Secondary Hypothesis I: The IYG will have significant improvements in quality of life, general health, physical functioning, perceived stress, anxiety, and sleep compared to the DYG.

These will be analyzed by the same methods as outlined for Primary Aim II (above).

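### The inflammatory-marker blood draw has no clock time and no interval since the last hot-yoga class, so a short-term class after-effect can enter the yoga arm only

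*Combined protocol and SAP*

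**What the plan says.** Hypothesis IIIa (sections 1.1 and 9.6) is that salivary cortisol, TNF-alpha, IL-6 and CRP "will significantly decrease, following 5- and 8-weeks of hyperthermic yoga in the IYG compared to the DYG".

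Section 9.5.2, to which the baseline visit refers for details of the markers, says "Inflammatory Markers: 30 mL of blood will be drawn per visit". It then describes tubes, centrifugation, storage and assays. It gives neither a time of day nor a relation to class days. The lists for Visit 5 (section 6.2.4) and Visit 6 (section 6.2.5) name the markers without adding a timing rule. On visit timing, section 6.2.4 says "Assessment visits will be completed within a reasonable time frame (+/- 3 workday window", and staff may go outside that window.

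Saliva is fixed by the clock, to handle diurnal variation: "four samples will be obtained prior to each cortisol assessment (nighttime [1 and 2] and waking [3 and 4". Salivettes forgotten at baseline are accepted later: "can bring to the following visit as long as it was collected at the right time period". That period is not defined in the readable text. Both schedules (6.1.1 and 6.1.2) mark salivary cortisol with an asterisk whose footnote is absent from the available text.

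The IYG is asked to take two or more classes a week for eight weeks (sections 3 and 5.1). The primary analyses use data from before the DYG crosses over (section 9.3). The adjustment planned for exposure is the number of classes attended (section 9.6, Adherence).

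Class times are partly captured. Participants write the date and time on the mood forms completed around each class (section 6.2.2), the sleep diary tracks exercise (section 9.5.2), and "The two yoga studios track attendance via computer systems" (section 5.4).

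**The concern.** A marker measured a few hours after 90 minutes of heated exercise may differ from the same person's level on a rest day. In the pre-crossover comparison only IYG samples can be taken in that state. Randomisation does not balance it, because it arises from the assigned treatment. Baseline samples precede the first class in both arms, so the after-effect would enter only the week-5 and week-8 values and hence the IYG slope. In the latent growth model that slope is the mediator.

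The rationale in section 2.2 gives some reason to expect short-term effects. It says "Recent data suggest that Bikram Yoga similarly raises core body temperature", cites faster return to sleep "on nights when yoga was practiced that day compared to non-yoga days", and suggests cytokines as a possible route for next-day mood change after induced fever. Section 6.2.2 collects forms to study acute mood change around each class. Nothing comparable is planned for the blood markers.

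An acute rise would mask a real decrease over the weeks. An acute fall would look like one. Class count does not separate these, since two people with the same count can differ by days in time since their last class.

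**Working it through.** **The plan's own power figure.** Section 9.2 gives 79% power at d = 0.70 and 50% at d = 0.50 (two-sided t-test, alpha 0.05, 32 per arm). The noncentral t gives 78.7% and 50.4%, so the figures reproduce. They concern the IDS-CR; no power is stated for the markers. They are used here only to set the sample size.

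**Inputs from the documents.**
- Requested minimum of 2 classes a week (sections 3 and 5.1).
- Adherence threshold of 12 of 16 classes in 8 weeks (section 5.4): 12/8 = 1.5 a week.
- 32 evaluable per arm (section 9.2).
- DYG study classes before crossover: none.

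**Assumptions, not in the documents.**
- Visit time is unrelated to class time, and after-effect windows do not overlap.
- The after-effect lasts 24 h (48 h as a variation) and is constant over that time.
- Its size a is 0.25, 0.5 or 1.0 SD of the marker.
- Three classes a week is shown as a higher-attendance case.

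**Share of IYG draws inside the window:** f = classes per week × window hours / 168.

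**Bias in the arm difference:** f × a, since the DYG share is taken as 0 and neither arm has had a class at baseline.

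| Classes a week | Window | f | a = 0.25 | a = 0.5 | a = 1.0 |
|---|---|---|---|---|---|
| 1.5 | 24 h | 36/168 = 0.214 | 0.05 SD | 0.11 SD | 0.21 SD |
| 2 | 24 h | 48/168 = 0.286 | 0.07 SD | 0.14 SD | 0.29 SD |
| 3 | 24 h | 72/168 = 0.429 | 0.11 SD | 0.21 SD | 0.43 SD |
| 2 | 48 h | 96/168 = 0.571 | 0.14 SD | 0.29 SD | 0.57 SD |

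**Scale.** With 32 per arm the standard error of a difference in SD units is √(2/32) = 0.25. A bias of 0.14 SD is 0.14/0.25, about 0.6 standard errors.

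**Effect on a two-sample t-test**, with mixture variance f(1−f)a² added to the IYG, at two classes a week and a 24 h window, for a = 0.25, 0.5 and 1.0 SD:
- No change over the weeks: two-sided rejection rate 6%, 9%, 19% instead of 5%.
- True decrease of 0.5 SD, after-effect opposing: power 39%, 28%, 13% instead of 50%.
- True decrease of 0.5 SD, after-effect in the same direction: 61%, 71%, 84%.

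With a 48 h window the no-change rejection rates are 9%, 20% and 57%. The t-test is a simplification, because the plan analyses the markers by latent growth curves.

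If every draw fell outside the after-effect, f would be 0, and the rejection rate and power would return to 5% and 50%. The sample size does not change.

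**The case against.** The other side has four good arguments.

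**Class times are recorded.** A reader might infer that recency is lost. It is not: the mood forms carry date and time, the studios log sign-ins, and the diary tracks exercise. Hours since the last class can largely be reconstructed. What stands is that no section links these records to the samples or plans an analysis with them.

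**Saliva may be covered.** A reader might infer that saliva also lacks any rule on class days. The documents do not support that conclusion. The cortisol footnote is missing from the available text, participants receive instructions with the salivettes, and a required collection period is mentioned. The blood markers do not depend on this.

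**The hypothesis does not say sustained.** It says markers will be lower after 5 and 8 weeks of yoga than in the control arm. If draws are unrelated to class days, the IYG mean estimates the average level while classes continue, and after-effects are part of the treatment effect. That is a legitimate target, but the plan does not state it. A mediator modelled as a slope over weeks is more naturally read as gradual change, and visit timing is not controlled so as to ensure a representative mix.

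**No marker evidence is cited for an acute change after a class.** The supporting material concerns temperature, sleep and mood. For shifts up to 0.5 SD over 24 h the bias is modest, and at lower attendance smaller still; section 8 tolerates single-class weeks. This stands, and it limits how strongly the point can be put.

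**Conclusion.** The point holds for the blood draw. The plan sets no time of day and no interval since class, only one arm can show a class after-effect before crossover, and the class-count covariate does not address recency. For saliva it is unconfirmed.

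The share of affected draws, about 29% within 24 h at two classes a week and about 21% at the adherence threshold, rests on visit time being unrelated to class time. The bias of about 0.07, 0.14 or 0.29 SD rests on assumed shifts of 0.25, 0.5 or 1.0 SD lasting 24 h. Direction is unknown and may differ by marker. The DYG share of zero assumes that controls take no yoga elsewhere; the inclusion criteria require willingness to keep exercise stable, but do not exclude this possibility outright.

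A reader might infer that Hypothesis IIIa will be biased by a known amount, or that the marker data will be uninterpretable. The documents support neither, because they contain no after-effect figure for any marker. This is an inexpensive improvement to one part of Aim III. It does not affect the IDS-CR comparison.

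**What to change.** 1. In section 9.5.2 and the Visit 5 and Visit 6 lists, schedule the blood draw on a non-class day, with a stated minimum interval since the last class (for example at least 24 h) and at a similar clock time within each participant.
2. Derive hours since the last class for every blood and saliva sample from the dated and timed class forms, checked against studio sign-in.
3. In section 9.6, prespecify a sensitivity analysis for Hypothesis IIIa that excludes samples inside the interval or adjusts for recency. State whether the target is change apart from the latest class or the average level while classes continue.
4. Check the cortisol footnote and the salivette instructions for a rule on class days.
5. Apply the same to Visits 10 and 11 only for the exploratory analyses that include crossover data.

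The cost is a line of visit instructions, a derived variable and one analysis, with slightly tighter scheduling in a trial that has already needed flexible visits. Draws that cannot meet the interval should still be taken and flagged, so that the rule does not create missing data. A 24 h interval may not remove longer after-effects; the recency analysis can examine those.
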